9.4. Definition and Use of Visit Windows in Reporting

For reporting purposes, the following visit windows will be used for efficacy, patient-reported outcomes and safety display that show by scheduled visits. If two or more observations fall into the same visit window, the observation closest to the target day will be used in the analyses. If there is a tie, the later observation will be used. However, for a subject who discontinues from the study early prior to the Week 48 visit and who does not have an observation within the Week 48 visit window, if two or more observations fall in the same visit window (ie, a visit window prior to Week 48), then the latest observation (rather than the observation closest to the target day) within this visit window will be used in the analysis for that visit window.

The visit windows will be applied to on-drug data and on-study data separately (see [Section 9.1](#)).

Table 5. Visit Windowing

Visit Label	Target Day ^a	Window Definition
Screening		< Day 1
Baseline	Day 1	Last non-missing assessment on or before Day 1 and prior to first dose of investigational product (ie, tofacitinib or placebo)
Week 2	Day 15	Day 2 to Day 21
Week 4	Day 29	Day 22 to Day 42
Week 8	Day 57	Day 43 to Day 70
Week 12	Day 85	Day 71 to Day 98
Week 16 ^c	Day 113	Day 99 to [Treatment Switch Day ^b or Day 140, whichever is smaller]
Week 24	Day 169	[Treatment Switch Day ^b +1 or Day 141, whichever is smaller] to Day 196
Week 32	Day 225	Day 197 to Day 252
Week 40	Day 281	Day 253 to Day 308
Week 48	Day 337	≥ Day 309

- a. Target day is equal to the target week×7 days + 1 day.
- b. Treatment switch day = day of the first dose of treatment switch at Week 16 (ie, treatment switch day = treatment switch date – date of the first dose +1), where treatment switch date is taken from the Oral Dosing CRF, as the start date in the first entry of the dosing log for the period of Week 16 to Week 24.
- c. All the data collected on treatment switch day will be counted in ≤ Week 16 except for the AE data. Any new treatment emergent AE occurred on the day of treatment switch will be counted in ≥ Week 24.

Note that the upper limit of the Week 16 visit window and the lower limit of the Week 24 visit window are defined uniquely for each of the subjects in the study regardless of which treatment group the subjects are randomized to, since per the study protocol, subjects randomized to the placebo → tofacitinib 5 mg BID treatment group will advance to the predetermined treatment (tofacitinib 5 mg BID) in a blinded fashion for the remainder of the study. Further details for the Week 16/Week 24 visit windows are in order.

1. If treatment switch day falls between Day 99 and Day 140, then the upper limit of the Week 16 visit window is the smaller of treatment switch day or Day 140 and the lower limit of the Week 24 visit window is the smaller of treatment switch day+1 or Day 141;
2. If treatment switch day < 99, >140, or missing, then the upper limit of the Week 16 visit window will be set to Day 140 and the lower limit of the Week 24 visit will be set to Day 141.

Effects of Bullets 1 and 2 above are further illustrated as follows.

Visit label	If treatment switch day is							
	Missing		<99		99-140		>140	
	Week 16	Week 24	Week 16	Week 24	Week 16	Week 24	Week 16	Week 24
Day window	99 to 140	141-196	99 to 140	141-196	from [99 to 99] up to [99 to 140]	from [100 to 196] up to [141 to 196]	99 to 140	141-196

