- Administer in-clinic dose of investigational product from previously dispensed study drug supplies.

The following procedures can be done before or after dosing depending upon the clinic's schedule but it is recommended that they be done at the same time (before or after dosing) consistently across all subsequent subject clinic visits:

- Targeted physical examination (examination of heart, lungs, abdomen, lower extremities, skin (presence of rash) and lymph nodes);
- Weight (without shoes preferred);
- BASMI (linear function) by qualified blinded assessor: Lateral spinal flexion, tragus-to-wall distance, lumbar flexion (modified Schober), maximal intermalleolar distance and cervical rotation;
- Spinal mobility obtained by qualified blinded assessor: chest expansion;
- Assessment of swollen joints (44-joint count) by qualified blinded assessor;
- Assessment of enthesitis using the MASES Index by qualified blinded assessor;
- Complete drug accountability.

After dosing:

- Monitoring of adverse events and concomitant treatments. Record any modifications, deletions or additions;
- Contraception check: Confirm and document that proper contraception is being used;
- Risk factor check for VTE ([Section 7.1.14](#));
- Contact IWRS and dispense new supply of study medication to subject;
- Instruct subject not to take the in-clinic dose of investigational product the day of the next study visit but to bring the drug supply with them to the visit.

6.2.10. Week 48

There is a ± 7 day window for this visit.

Subjects are required to fast for at least 9 hours prior to the visit; however, blood collection for laboratory testing may be taken up to 48 hours prior to or following this visit as necessary to ensure the samples are collected in a fasting state. If the blood collection is completed in advance of the clinic visit, the PROs should not be done with the blood collection but at the clinic visit.

- All PROs should be performed before any other study procedures at the clinic visit. These include the following: ASAS/ASDASCRP Component: “Patient Global Assessment of Disease (NRS)”, “Patient Assessment of Spinal Pain” which includes Total Back Pain (NRS) and Nocturnal Spinal Pain (NRS), BASDAI (NRS), BASFI (NRS), ASQoL, SF-36v2, EQ-5D-3L and EQ-VAS, FACIT-F, WPAI and AS-HCRU Questionnaire;
- Vital signs: Blood pressure (seated), pulse rate and temperature (via tympanic, oral or temporal, preferred);
- 12-lead electrocardiogram submitted to central reader;

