6.3. Follow-up Visit

The Follow-up visit is required of all subjects who complete the study or are withdrawn from the investigational product after the Week 40 visit. These subjects must have a Follow-up visit within 28 days (± 7 days) of the Week 48 visit. Subjects who are withdrawn from the investigational product prior to the Week 40 visit are not required to have a follow-up visit after they complete the study at the Week 48 visit. There is a ± 7 day window for this visit.

All subjects who complete or discontinue early from the investigational product after Week 40 must have a Follow-up visit within 28 days (± 7 days) of the Week 48 visit.

Subjects are required to fast for at least 9 hours prior to the visit; however, blood collection for laboratory testing may be taken up to 48 hours prior to or following this visit as necessary to ensure the samples are collected in a fasting state.

The following procedures will be performed:

- Targeted physical examination (examination of heart, lungs, abdomen, lower extremities, skin (presence of rash) and lymph nodes);
- Weight (without shoes preferred);
- Specific Medical History: History of uveitis, psoriasis, inflammatory bowel disease and peripheral articular involvement as assessed by swollen joint count;
- Vital Signs and temperature: Blood pressure (seated), pulse rate and temperature (via tympanic, oral or temporal, preferred);
- Laboratory testing: Central laboratory tests include: Hematology, Urinalysis, Chemistry Panel, Lipid Profile (fasting), Urine Pregnancy Test (for women of childbearing potential only), hsCRP;
- Adverse event reporting and concomitant treatment use;

- Risk factor check for VTE ([Section 7.1.14](#));
- Contraception check: Confirm and document that proper contraception is being used.

If abnormalities in hematology or chemistry results or adverse events with a causal relationship to the study medication are still observed/ongoing at the follow-up visit, the subject must continue to be followed until the laboratory abnormality or adverse event stabilizes or returns to baseline levels as approved by the Sponsor.

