9. APPENDICES

9.1. Data Set Description: On-Drug vs. On-Study Data

If for any reason, when subjects have prematurely and permanently discontinued the investigational product (ie, tofacitinib or placebo) during the course of the study, every effort will be made by the study sites and investigators to engage these subjects to follow through the remaining planned study visits and to collect both efficacy and safety data through the end of the study while they are off-drug. It is important that subjects are still blinded to the treatment they receive through the end of the study. For a subject who prematurely discontinues the investigational product (ie, tofacitinib or placebo), the date of the permanent drug discontinuation as recorded on the Disposition – End of Treatment CRF page will be used to separate the efficacy data collected in visits on or before this date as this subject's on-drug data and data collected in visits after this date as this subject's off-drug data.

Because of this data differentiation, there will be two different datasets included for analyses. The first dataset, referred to as On-Drug Data, includes only data that are collected in visits on or before the permanent drug discontinuation. The second dataset, referred to as On-Study Data, includes both the data collected in visits on or before as well as visits after the permanent drug discontinuation. Data that are collected during the on-drug period will be flagged as on-drug data and data collected during the off-drug period will be flagged as off-drug data. Therefore, both on-drug and off-drug data constitute the on-study data. All of the analyses specified in this SAP will use the On-Drug Data unless otherwise specified when using the On-Study Data. The On-Study data will only be used for specific supportive analyses of the primary endpoint (ASAS20), key secondary endpoint (ASAS40) and their 4 components (see [Section 2.1](#), [Section 6.1.2](#) and [Section 6.2](#)) as well as other Type I error controlled secondary endpoints.

All safety data will be analyzed regardless of investigational product discontinuation.

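### SAP Table 5 leaves the Week 48 window open-ended with no Follow-up row, so an off-treatment Follow-up value is reported as Week 48 when the Week 48 value is missing or its visit was well early

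*SAP*

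**What the plan says.** SAP Section 9.4 states that "the following visit windows will be used for efficacy, patient-reported outcomes and safety display that show by scheduled visits". Its Table 5 ends with Week 48: target Day 337, window Day 309 onward. No upper day is given and no row follows. Two selection rules apply within a window. The first is "If two or more observations fall into the same visit window, the observation closest to the target day will be used in the analyses"; the second is "If there is a tie, the later observation will be used". The section adds: "The visit windows will be applied to on-drug data and on-study data separately".

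SAP Section 9.1 separates on-drug from off-drug efficacy data by a date taken from the end-of-treatment page. That sentence opens "For a subject who prematurely discontinues the investigational product (ie, tofacitinib or placebo), the date of the permanent drug discontinuation" and so concerns early stoppers. No date is stated for subjects who complete treatment. The same section says that safety data are analyzed whether or not the subject stopped investigational product.

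Protocol Section 6.3 says the "Follow-up visit is required of all subjects who complete the study or are withdrawn from the investigational product after the Week 40 visit". The visit is due 28 days, give or take 7, after Week 48. It collects hematology, chemistry, fasting lipids, urinalysis, hsCRP, vital signs and weight. In Protocol Section 6.2.10 the Week 48 visit has its own tolerance ("There is a ± 7 day window for this visit"), and a completer takes a dose in clinic at that visit. No drug is dispensed at Week 48, so this is the last dose.

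SAP Section 6 includes Follow-up data in the Week 48 analysis. SAP Section 6.6.2 summarizes laboratory tests and vital signs by treatment group and visit.

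**The concern.** A Follow-up value differs in kind from a Week 48 value. Protocol Section 1.2.4 gives a terminal half-life of about 3 hours, so a sample 28 days after the last dose is off treatment. Protocol Section 1.2.3.2 reports that changes in blood counts, LDL, creatinine and transaminases usually or generally reversed after stopping. Protocol Section 9.3 gives special attention to several of these parameters. A Follow-up value under a Week 48 label would therefore tend to understate on-treatment change. For hsCRP it would tend to misstate the Week 48 response.

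There is also a loss of information. With no row of its own, a Follow-up value that is not chosen for Week 48 is not shown at any visit, so recovery after stopping is not visible in the by-visit tables.

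**Working it through.** **1. Target day.** The SAP's formula is "Target day is equal to the target week×7 days + 1 day". For Week 48: 48 × 7 + 1 = 337, as in Table 5. The other eight target days reproduce too.

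**2. Where the samples fall.** Inputs: Week 48 tolerance ±7 days and a blood-draw allowance of 48 hours either side (Protocol 6.2.10); Follow-up 21 to 35 days after Week 48, with the same draw allowance (Protocol 6.3).

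| | Visit | Blood sample |
|---|---|---|
| Week 48 | 337 ± 7 = Day 330 to 344 | Day 328 to 346 |
| Follow-up | 330 + 21 to 344 + 35 = Day 351 to 379 | Day 349 to 381 |

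The earliest Follow-up sample (Day 349) is after Day 309, so every in-tolerance Follow-up sample lies in the Week 48 window.

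**3. Both values present and in tolerance.** Let v be the Week 48 visit day, g the gap to Follow-up, and a and b the draw offsets (−2 to +2). The Follow-up sample is always after Day 337. Its distance from target minus that of the Week 48 sample is:

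- Week 48 sample before Day 337: 2v + g + a + b − 674. The minimum is 660 + 21 − 2 − 2 − 674 = 3 days.
- Week 48 sample on or after Day 337: g + b − a. The minimum is 21 − 2 − 2 = 17 days.

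The difference is always positive. Enumerating all 15 × 15 × 5 × 5 = 5,625 combinations agrees: the Follow-up value is chosen in none.

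**4. Week 48 visit early.** With the visit e days early and both samples drawn on the visit day, Follow-up is |g − e| days from target and Week 48 is e days. Follow-up is chosen when |g − e| ≤ e, that is e ≥ g/2, because ties go to the later value.

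| Gap g | Condition | Follow-up chosen if the Week 48 visit is on |
|---|---|---|
| 21 days | e ≥ 10.5, so 11 | Day 309 to 326 |
| 28 days | e ≥ 14 | Day 309 to 323 |
| 35 days | e ≥ 17.5, so 18 | Day 309 to 319 |

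All of these lie beyond the 7-day tolerance. A visit before Day 309 falls in the Week 40 window, which leaves Week 48 without its own value.

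**5. Week 48 value missing.** The Follow-up value is the only one in the window and becomes the Week 48 value.

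**6. On-drug status.** Safety laboratory and vital-sign values carry no on-drug flag, so for them the fault is the visit label alone. Efficacy hsCRP is split, but the stated cut-off covers only premature discontinuers. Their later samples are already off-drug. For completers nothing explicit removes a Follow-up hsCRP from the on-drug Week 48 model.

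**7. Which upper limit would work.** Day 346, 347 or 348 keeps every in-tolerance Week 48 sample and excludes every in-tolerance Follow-up sample. Day 344 would lose Week 48 draws on Days 345 and 346. Day 350 would admit Follow-up draws on Days 349 and 350. A roughly symmetric window ending on Day 364 would still admit Follow-up visits on Days 351 to 364.

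**The case against.** The strongest reply is that the closest-to-target rule already protects the Week 48 result. That is right whenever an in-tolerance Week 48 value exists. A reader might infer that Follow-up values routinely displace real Week 48 values; step 3 shows that they do not. Displacement needs a visit at least 11 days early, which is outside the protocol's own tolerance.

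A reader might also infer that laboratory values would be reported as on-drug. They would not, since Section 9.1 applies no such split to safety data. Nor does the SAP say that a completer's Follow-up hsCRP is on-drug; that reading comes from silence. Section 9.1 also describes on-drug data generally as data collected up to permanent discontinuation of drug. If a completer's final dose were treated as that date, Follow-up hsCRP would be off-drug. The SAP also lists change in hsCRP only through Week 48. What stands is that the cut-off for completers is left to the programmer.

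Finally, recovery after stopping is not a stated objective, and laboratory summaries follow sponsor standards that are not part of these documents and may show Follow-up separately. That tempers the point about lost Follow-up data. It does not change Table 5, which governs safety displays by visit and has no place for those values.

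**Conclusion.** The gap is real but minor. As Table 5 is written, an off-treatment Follow-up value becomes the Week 48 value in two situations: the Week 48 value is missing, or its visit was early by the margins in step 4. In every other in-tolerance case the Week 48 value is kept and the Follow-up value drops out of the by-visit displays.

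The reach is limited. The Week 16 analysis uses efficacy data only through Week 16 and is definitive, so the primary, key secondary and other Type I error controlled endpoints are untouched. SAP Section 5 calls all Week 48 results secondary, and both arms take tofacitinib by then. Patient-reported outcomes and BASMI are not collected at Follow-up, so ASAS20, ASAS40, BASDAI, BASFI and FACIT-F cannot be affected. ASDAS-CRP and ASAS 5/6 could be affected only if a Follow-up hsCRP were paired with Week 48 values of the other components.

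The documents give no rate of missing or early Week 48 samples, so the number of subjects involved is unknown. The conclusion assumes that windows are assigned by study day, as Section 9.4 states, and not by nominal visit.

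**What to change.** In SAP Table 5, add a Follow-up row and assign to it any sample that carries the nominal Follow-up label. Alternatively, cap Week 48 at a fixed day between 346 and 348. The nominal label is the safer choice, because a fixed cap would also shut out a genuine Week 48 visit held late.

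Do not tie the upper limit of Week 48 to the last dose. Subjects who stop drug early are followed through all scheduled visits (Protocol Section 6.4), and their data feed the Week 48 on-study ASAS20 and ASAS40 analyses (SAP Table 8) and the safety displays. For a subject who stopped at Week 20 (20 × 7 + 1 = Day 141), such a window would close long before it opens at Day 309.

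In SAP Section 9.1, state that for completers efficacy samples taken after the last dose are off-drug, with an allowance for Week 48 blood drawn within 48 hours of that visit.

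The cost is a few lines of SAP text and the matching programming. No new data are needed.

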6.4.1. Monitoring Criteria

The following laboratory abnormalities require prompt retesting, ideally within 3- 5 days:

- Any single hemoglobin value that drops >2 g/dL (or 20 g/L) below baseline, if indicated after review by the Pfizer Medical Monitor or investigator. Factors that will be considered include stability of hemoglobin values, and their relationship to the standard reference range;
- Absolute neutrophil count $<1.2 \times 10^9/L$ ($<1200/mm^3$);
- Absolute lymphocyte count $<0.5 \times 10^9/L$ ($<500/mm^3$);
- Platelet count $<100 \times 10^9/L$ ($<100,000/mm^3$);
- Serum creatinine increase $>50\%$ over the average of screening and baseline values OR an absolute increase in serum creatinine >0.5 mg/dL (or 44 $\mu\text{mol/l}$) over the average of screening and baseline values, if indicated after review by the Pfizer Medical Monitor or investigator. Factors that will be considered include stability of the creatinine values, and their relationship to the standard reference range;
- Any creatine kinase (CK) $>5x$ upper limit of normal (ULN) (repeat laboratory testing should also include cardiac troponin).

If the abnormality is confirmed after re-test, follow-up should be discussed with the Sponsor and frequency of monitoring increased. Confirmation should be done based upon central laboratory results, but local laboratory results will be acceptable, particularly if these may be done more promptly.

For additional laboratory abnormalities that require prompt retesting, preferably within 48 hours from awareness of the abnormal results see [Section 8.3.2](#) Potential Cases of Drug-Induced Liver Injury.

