5. GENERAL METHODOLOGY AND CONVENTIONS

There will be a total of 2 planned analyses conducted when all applicable subjects have completed their Week 16 and Week 48 (including follow-up) visits, respectively. The investigators, subjects and sponsor study team will remain blinded to the first 16 weeks of treatment assignment through the entire duration of the trial until database release at Week 48. The Week 16 analysis will include all efficacy data through Week 16 and the safety data through the data cutoff date (for those subjects who have passed the Week 16 visit). As the primary endpoint (ASAS20), the key secondary endpoint (ASAS40) and the other Type I error controlled secondary endpoints are at Week 16, there will be no additional adjustment made for Type I error rate at the final analysis at Week 48. The efficacy analysis results through Week 16 obtained from the Week 16 analysis will be considered final and definitive. CCI

The Week 48 analysis will be conducted when all the applicable subjects have completed their Week 48 (including follow-up) visit and the database is released. All the Week 48 analysis results will be secondary in nature. The Week 48 analysis will contain results for earlier visits prior to or at Week 16 including those for the primary endpoint and the key secondary endpoint; however, they will serve as a sensitivity analysis only to ensure there are

no major changes to the definitive results for the primary endpoint and the key secondary endpoint obtained at the Week 16 analysis.

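### For subjects who leave the study early, SAP 9.4 takes the latest value in any earlier window with repeat observations, so a completed visit's value can depend on later dropout (minor)

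*SAP*

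**What the plan says.** SAP 9.4 sets the windows for efficacy, patient-reported and safety displays by scheduled visit, and applies them separately to on-drug and on-study data. When several observations share a window, "the observation closest to the target day will be used in the analyses"; for equal distances, "If there is a tie, the later observation will be used".

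An exception follows. It covers the case "for a subject who discontinues from the study early prior to the Week 48 visit and who does not have an observation" in the Week 48 window. The condition on windows is "if two or more observations fall in the same visit window (ie, a visit window prior to Week 48", and the instruction is "then the latest observation (rather than the observation closest to the target day". No wording ties this to the window in which the subject left, and no wording exempts Week 16 or earlier visits. The SAP's version history records that windowing for these subjects was clarified in version 2, but gives no reason for preferring the latest value.

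Two other provisions matter. SAP 5 states: "The efficacy analysis results through Week 16 obtained from the Week 16 analysis will be considered final and definitive". It then has the Week 48 analysis repeat the earlier visits, as a sensitivity check that nothing major has changed. For a subject whose treatment switch falls between Day 99 and Day 140, SAP 9.4 also says that "the upper limit of the Week 16 visit window is the smaller of treatment switch day or Day 140".

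**The concern.** A rule that picks the value for a completed visit should use only what was known about that visit. Here two subjects with identical observations in the Week 12 window can be given different Week 12 values because one of them left the study months later.

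This has two consequences. First, by-visit summaries mix two selection rules, with the mix decided by a post-randomization outcome. Second, the Week 48 re-run is meant to confirm the Week 16 result. A subject who leaves after the Week 16 data cut can change value in that re-run although no data were corrected, so a windowing artefact can look like a data change. In the Week 16 analysis itself only departures known at the cut could trigger the exception, so its use would also depend on how long a subject had been followed by then.

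Repeat observations are most likely in laboratory data. Protocol 6.4.1 says that certain "laboratory abnormalities require prompt retesting, ideally within" 3-5 days, and the Schedule of Activities allows unplanned visits.

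**Working it through.** **Inputs.** Target days and windows: SAP Table 5. Visit tolerances (±3 days to Week 4, ±7 days after): Protocol Schedule of Activities. Planned size (240, 120 per arm): Protocol 9.1 and Section 3. The documents give no rate of study dropout or of repeat observations.

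**1. Target days.** The SAP formula is week × 7 + 1. Week 4: 4 × 7 + 1 = 29. Week 12: 85. Week 16: 113. Week 24: 169. All match Table 5.

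**2. Does the exception act on scheduled visits?** A Week 16 visit on schedule falls on Days 113 ± 7 = 106-120, inside Days 99-140. A Week 4 visit falls on Days 29 ± 3 = 26-32, inside Days 22-42. The same holds at every other visit. With one observation per window, latest and closest are the same value, so the exception acts only where an unplanned, repeat or off-schedule observation exists.

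**3. How far can the chosen value move?** Window end minus target: 21 − 15 = 6 days at Week 2; 13 days at Weeks 4, 8 and 12 (for example 98 − 85); 27 days at Weeks 16 to 40 (for example 140 − 113). These are outer limits. A retest at the 3-5 days the protocol aims for would lie days, not weeks, from the first value.

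**4. The rule applied literally to constructed cases.**

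| Window | Observation days | Distance from target | Chosen if subject stays | Chosen if subject later leaves |
|---|---|---|---|---|
| Week 4 (target 29) | 29, 33 | 0, 4 | 29 | 33 |
| Week 12 (target 85) | 85, 97 | 0, 12 | 85 | 97 |
| Week 12 (target 85) | 81, 85 | 4, 0 | 85 | 85 |
| Week 16 (target 113), switch Day 118 | 112, 118 | 1, 5 | 112 | 118 |
| Week 16 (target 113), no switch day | 113, 138 | 0, 25 | 113 | 138 |
| Week 24 (target 169), switch Day 113 | 117, 169 | 52, 0 | 169 | 169 |

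Rows 1, 2, 4 and 5 show the dependence on later dropout. Row 3 shows that the general rule may itself select the second value. Row 6 is a retest after an on-schedule Week 16 visit: it falls in the Week 24 window, and both rules then choose the Week 24 visit.

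**5. The two analyses.** Take row 4 and let the subject leave after Week 32, after the Week 16 cut. The Week 16 analysis uses Day 112; the Week 48 re-run uses Day 118. The Week 16 data are the same in both.

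**6. Size, on assumed rates.** Exposed subjects in a given window = 240 × proportion leaving × proportion of those with a repeat. Low: 240 × 0.05 × 0.01 = 0.12. High: 240 × 0.15 × 0.10 = 3.6. This is an upper count, since the two rules sometimes agree. For ASAS20, one changed response moves an arm by 1/120 = 0.83 percentage points, and only if the two assessments differ in response status.

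**The case against.** The rule is prespecified and the same in both arms, and the Week 48 re-run of Week 16 is labelled sensitivity only. Week 16 is also largely protected. Under Protocol 6.2.6 the first open-label dose is given at the Week 16 visit after the assessments, so the window normally closes that day. A second observation inside it would usually be an earlier, unplanned one, and the latest value would then be the scheduled visit. Row 4 is that case if dosing followed the protocol. All of this stands, and it limits the size of the point.

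A reader might infer that the exception hides laboratory abnormalities in the subjects most likely to leave. The documents do not support that:

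- The trigger is leaving the study, not stopping the drug. Protocol 6.4 keeps subjects who stop the drug in scheduled visits. SAP Table 3 lists adverse events as a reason for stopping the drug; the study-discontinuation reasons in Table 4 do not name them.
- Most laboratory stopping criteria in Protocol 6.4.2 need two sequential abnormal values. For a subject who meets one on retest, the latest value shows the abnormality.
- The general rule takes the value closest to target, not the scheduled value, so subjects who stay can also be represented by a retest.
- Under Protocol 8.2.2, abnormal findings that prompt further diagnostic testing, intervention or stopping the drug are recorded as adverse events, outside the windowing.

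These arguments do not supply the missing limit on the exception, or a reason why a completed window should be re-selected after a later departure.

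**Conclusion.** The point holds as a minor flaw in the definition of a rule. As written, the value at a completed pre-Week-48 visit with two or more observations depends on whether the subject later leaves the study, and the Week 16 and Week 48 analyses can disagree for one subject on unchanged data.

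The expected effect is a few subjects at most, mainly in by-visit laboratory displays outside the Week 16 window. The range of 0.12 to 3.6 subjects per window rests entirely on assumed rates of 5-15% leaving and 1-10% with a repeat.

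A reader might go further and infer that the primary ASAS20 result is threatened, because the windows also govern on-drug data. The documents do not support this. Efficacy is assessed at scheduled visits that fall in their own windows, the Week 16 window normally closes on the switch day, and departures after the cut can alter only the sensitivity re-run. No direction of bias between arms is shown.

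**What to change.** Reword the exception in SAP 9.4 so that the latest observation is used only in the single window containing the study discontinuation date. In all other windows, use the observation closest to the target day for all subjects, with ties going to the later value. Selection in completed windows is then the same in the Week 16 and Week 48 analyses.

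The cost is one sentence in the SAP and a small programming change. No new data are needed, and no endpoint, model or testing order changes.
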